8 STUDY ADMINISTRATION

8.1 Treatment Assignment Methods

8.1.1 Randomization

Participants will be randomized to one of the two condition groups. A statistician who is not involved with enrolling subjects will be responsible for creating the randomization chart. We will do block randomization for 4 assignments at a time. Each block will contain the two arm assignments repeated once in a random order. We will create a string that is 250 assignments long. As participants reach the intervention phase they will be assigned to the next available assignment in this string. Once an assignment has been used it is no longer available to be used. Study staff and participants will not be blinded to the condition. Individuals conducting data analyses will use data which blinds them to which group participants are in..

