2.1 Primary Objective (or Aim)

The primary objective of this study is to compare measures of acceptance and feasibility of teen-parent dyads randomized to bidirectional teen-parent vs. teen only monitoring of cellphone use while driving in an on-road driving study.

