3.3 Study Duration, Enrollment and Number of Sites

3.3.1 Duration of Study Participation

The study duration per subject pair will be up to eight weeks.

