3.3.2 Total Number of Study Sites/Total Number of Subjects Projected

The study is being conducted at the Children's Hospital of Philadelphia and the University of Pennsylvania. It is expected that a maximum of 250 people will participate in this research study.

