3.4 Study Population

3.4.1 Inclusion Criteria

Teen:

- 1) Is a high school student (age 16 or 17 at start of the study)
- 2) Holds a valid driver's license
- 3) Lives in parent/guardian's home
- 4) Primarily drives one car
- 5) Drives an average of 4 or more trips per week
- 6) Has their own iPhone 4S or newer or Android 4.3 or newer smartphone with data plan
- 7) Admits to texting while driving at least once in the last month

Parent:

- 1) Is the parent of a teen driver
- 2) Drives an average of 4 or more trips per week
- 3) Primarily drives one car
- 4) Has their own iPhone 4S or newer or Android 4.3 or newer smartphone with data plan

5) Admits to texting while driving at least once in the last month

Both parent and teen will be enrolled together as a pair.

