6.4.1 Teen-Parent Monitoring Group

The blocking settings will turn on by default while driving. Blocking settings will be pre-set to block all incoming calls and text messages while the vehicle is in motion, but participants will have the ability to override the blocking. Number of unlocks can be monitored through logging in to the Cellcontrol website.

In the bidirectional monitoring arm, the teen will receive an email notification when their parent unlocks their phone while driving and vice versa.

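### Upcoming assignments are not protected from staff who can stop a dyad before randomisation; as a minor point, section 8.1.1 should say that a dyad takes one assignment

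*Combined protocol and SAP*

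**What the plan says.** **Assignment and access.** Section 8.1.1 has a statistician outside enrolment create the chart, in blocks of four with two assignments per arm. Assignment comes at the end of baseline: "As participants reach the intervention phase they will be assigned to the next available assignment in this string". Sections 3.2 and 8.1.1 leave participants and staff unblinded; section 8.1.1 blinds those who analyse the data. Section 3.2 keeps the chart on a secure server open to key personnel, without saying who they are. No section says who looks up or releases the next assignment.

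**What surrounds it.** Baseline is weeks 1 to 3 (section 3.1.2). Investigators may discontinue participants at their discretion at any time (section 4.4). Drive data are not followed live but may be viewed after a drive ends (section 4.3.1). The intention-to-treat set consists of subjects randomised at the start of the intervention period (section 6.3.2).

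**Unit.** Section 8.1.1 assigns participants, and "Once an assignment has been used it is no longer available to be used". On length it says "We will create a string that is 250 assignments long", while section 3.3.2 says "It is expected that a maximum of 250 people will participate in this research study". Elsewhere the unit is the pair. The primary objective (section 2.1) compares "teen-parent dyads randomized to bidirectional teen-parent vs. teen only monitoring of cellphone use while driving", and the abstract and section 2.2 use the same unit. Section 3.3.1 says "The study duration per subject pair will be up to eight weeks" and section 3.4.1 says "Both parent and teen will be enrolled together as a pair". Section 6.4.1 defines its arm across both members: "In the bidirectional monitoring arm, the teen will receive an email notification when their parent unlocks their phone while driving and vice versa". Section 6.4.2 does likewise.

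**The concern.** Concealment has two parts: making the list independently, and keeping the next entry from anyone who can influence whether or when the next unit is randomised. The plan covers the first part but not the second.

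The usual worry, that foreknowledge shapes who is enrolled, has little force here because eligibility is settled before baseline. The opening is later, between baseline and assignment. There, a person who knows or can infer the next arm could affect which dyads go forward, and in what order. A dyad stopped at that point has no arm, so it appears neither in the intention-to-treat set nor in retention by arm, and the planned tables would not reveal a pattern. If such stops depended on both baseline phone use and the next arm, the by-arm phone-use figures that section 2.2 intends for designing a larger trial would be distorted.

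The minor point concerns wording. The only operational rule speaks of participants, each of whom has an individual study ID (section 8.2.1). The arms can be delivered only if teen and parent hold the same assignment, and no sentence says that they share one.

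**Working it through.** **Inputs.** Blocks of four, two per arm, and unblinded staff (section 8.1.1); cap of 250 people (section 3.3.2); enrolment in pairs (section 3.4.1). The plan gives no power or sample-size calculation, so none can be reproduced.

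**1. List length, the one stated figure.** One slot per person: 250 × 1 = 250, which matches the list. One slot per dyad: 250 / 2 = 125, which does not. The plan does not derive the length, so the match fits a per-person reading without proving it.

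**2. What can be known by tracking past assignments.** A 2:2 block of four has six equally likely orders. Assume a person who knows the block size and has seen every earlier assignment in order.

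| Slot in block | Chance it is certain in advance | Chance of a correct best guess |
|---|---|---|
| 1 | 0 | 1/2 |
| 2 | 0 | 2/3 |
| 3 | 1/3 (first two alike: 2 of 6 orders) | 1/3 × 1 + 2/3 × 1/2 = 2/3 |
| 4 | 1 | 1 |

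- Known share: (0 + 0 + 1/3 + 1) / 4 = 1/3.
- Correct guesses: (1/2 + 2/3 + 2/3 + 1) / 4 = 17/24 = 0.708, against 0.50 by chance.
- At the cap, 125 dyads make 31 whole blocks plus one dyad: 31 × 4/3 = 41.3, so about 41 of 125 assignments are known in advance. This is a ceiling, because every stop during baseline lowers the number assigned.
- A person who can open the chart knows every assignment.

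**3. Where that knowledge could act.** Consent, eligibility and device distribution come first (sections 4.1 and 5.1), then three weeks of baseline, then assignment, where the intention-to-treat set begins. Two things remain open to influence between baseline and assignment: whether a dyad proceeds (section 4.4 allows discontinuation at any time), and the order in which dyads take the next slot.

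**4. Effect of varying the block.** A 3:3 block of six has 20 orders. Slot 4 is certain in 2/20, slot 5 in 8/20, and slot 6 always: (0.1 + 0.4 + 1) / 6 = 1/4, against 1/3 for a block of four. Not disclosing the sizes can only reduce certainty further. The largest imbalance if the trial ends mid-block is half the block: 3 dyads for a block of six, 2 for a block of four.

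**5. Unit.** The abstract, sections 2.1, 2.2 and 3.4.1, and both arm definitions need one assignment per dyad. Sections 3.2 and 8.1.1 speak of participants. With one slot per dyad, both members share an arm by construction.

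**The case against.** **On concealment.** Real safeguards exist: a list made outside enrolment, sequential single-use slots, a restricted server and blinded analysts. Section 8.2.1 also limits an investigator or statistician who logs in to non-identifiable data. These count, but they do not close the route. Analyst blinding acts after selection. Independence in making the list does not govern who reads it. Study IDs link the data, and section 8.2.2 lets study team members upload device data by hand.

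It is also fair to say that dyads stopped before assignment are absent from by-arm retention simply because randomisation follows baseline. That is a feature of the design, not a fault; it means only that the tables could not show selective stopping.

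The stakes are limited. This is a pilot with descriptive primary endpoints, and two of the five (the proportion of eligible people who enrol, and enrolment per month) are settled before assignment.

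A reader might infer that selection is likely, or try to count the dyads affected. The documents support neither. They do not say that anyone tracks assignments, that enrolling staff have chart access, or how often anyone would act on what they knew.

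**On the unit.** The objectives already say that dyads are randomised, and the arms permit nothing else. A reader might take 8.1.1 literally and infer that half (unrelated slots) to two thirds (4 of 6 orders, adjacent slots in one block) of pairs would be split. That describes a reading the rest of the protocol excludes. The reference to all subjects randomised in section 6.3.2 is likewise correct once both members carry the dyad's arm.

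**Conclusion.** The concealment point stands as a cheap improvement. The plan does not bar staff who enrol, discontinue or assign from seeing or inferring the next assignment, and it places assignment after a period in which a dyad can be stopped at discretion. One third of assignments would be known, and 71% guessed correctly, by someone who knows the block size and has seen every earlier assignment in order; with chart access, all would be known. These figures measure predictability, not bias. Bias would also require someone to act on the knowledge in a way related to baseline phone use, which the documents neither show nor rule out. It would fall mainly on the secondary by-arm estimates intended for planning, so the gain from fixing it is modest.

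The unit point is a clarification. The wording of 8.1.1 should be reconciled with the objectives and arms, but the dyad is the only workable reading and no split pairs are expected.

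**What to change.** **Main change, in sections 3.2 and 8.1.1.** State that:
- staff who enrol, discontinue or assign participants cannot see upcoming assignments;
- each assignment is released only once the dyad is confirmed to start the intervention phase, by a named holder such as the independent statistician;
- block sizes vary (for example 4 and 6) and are not disclosed to staff. The actual sizes should sit in a document held by the statistician, not in the protocol.

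**Minor change, in sections 8.1.1 and 6.3.2.** State that teen and parent share one assignment, and that both are analysed in that arm.

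**Cost.** A few sentences, no new data and no change in sample size. The largest possible imbalance rises from 2 to 3 dyads. Who operates the list changes slightly: the plan describes no randomisation function in Way to Health, so the release step needs a named owner.

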8.2 Data Collection and Management

Confidentiality, Security, and Anonymization

8.2.1 Way To Health

All personal information that the participant is asked to provide will be collected via *Way To Health*. *Way To Health* collects subjects' names, dates of birth, addresses, email addresses, phone numbers, and the last four digits of their social security number. They also request the name and phone number of an alternate contact. To assure that participant confidentiality is preserved, individual identifiers are stored in a single password protected system that is accessible only to study research, analysis and IT staff. The last four digits of participants' social security numbers will be stored in a locked cabinet to be destroyed at a later date. An investigator or statistician who logs in will be able to access only non-identifiable data. The *Way To Health* administrative group and research coordinators responsible for contacting participants for follow-up study visits or responding to questions about the study are able to view participant names and contact information. The WTH web development team and Project Director currently have administrative access to PHI. All of these personnel will have completed Human Subjects Protection and HIPAA privacy training. The system automatically generates logs of all data queries which can be reviewed by research staff to ensure that no unauthorized persons have gained access to identifiable information. This system is hosted on site at The University of Pennsylvania (UPenn) and is protected by a secure firewall and several layers of operational security. Once a participant has been entered into this system, they are given a unique study identification number (ID). Any datasets and computer files that leave the firewall are stripped of all identifiers and individuals are referred to by their study ID. The study ID is also used on all analytical files.

The Penn Medicine Academic Computing Services (PMACS) is the hub for the hardware and database infrastructure that supports the project and the *Way To Health* web portal is built on this infrastructure. The data collected for *Way To Health* based studies is stored in mySQL databases on a PMACS-operated blade server environment devoted specifically to *Way To Health*. The data center is housed in Information Systems and Computing at [name]. All data are stored in a single relational database, allowing researchers to correct mistakes. Every SQL transaction, including accessing and changing data, is logged for auditing purposes. Data are entered into the database through several different mechanisms. Participants enter their own personal information and respond to surveys through a PHP-based web interface. Researchers have a separate interface that allows them to manually enter data if needed. Datasets are stripped of all personally identifiable information when exported for analysis. The web application automatically removes all identifiers when a researcher requests an analytic dataset. The only people with access to identifiable participant information are pre-specified Research Coordinators responsible for contacting participants for follow-up. Personal information and research data will be stored in separate SQL tables and will be linked by a computer-generated ID number. Additionally, any information that leaves this system to communicate with third party data sources (i.e. survey software) is stripped of any identifiers and transmitted in encrypted format. The same unique study ID is used to link these outside data to the participants. All data for this project will be stored on the secure/firewalled servers of the PMACS Data Center, in data files that will be protected by multiple password layers. These data servers are maintained in a guarded facility behind several locked doors, with very limited physical access rights. They are also cyber-protected by extensive firewalls and multiple layers of communication encryption. Electronic access rights are carefully controlled by UPenn system managers.

Way To Health uses highly secure methods of data encryption for all transactions involving participant's financial information using a level of security comparable to what is used in commercial financial transactions. This multi-layer system of data security, identical to the system protecting the University of Pennsylvania Health Systems medical records, greatly minimizes the risk of loss of privacy. All communications between users and our site will be encrypted with SSL/HTTPs technology.

8.2.2 Cellcontrol

Data collected by Cellcontrol through the DriveID device will be manually uploaded by members of the study team or directly to Way to Health through secure CSV reports. Data will not be tracked in real time.

8.2.3 Semi-Structured Interview

The semi-structured interview will be completed by a member of the study team and will be recorded by Penn's Mixed Methods Research Lab. The MMRL provides verbatim transcription of individual and group data through *Accurate, Dependable, Affordable* (ADA) transcription services. ADA provides secure and confidential data transfers consistent with the University of Pennsylvania's Institutional Review Board data safety standard. ADA provides transcription services that are also consistent with federal Health Insurance Portability and Accountability Act (HIPAA) guidelines and regulations. The MMRL works with ADA to check for accuracy. Once accuracy in transcription is determined, original recordings are destroyed.

8.3 Confidentiality

All data and records generated during this study will be kept confidential in accordance with Institutional policies on subject privacy and the Investigator and other site personnel will not use such data and records for any purpose other than conducting the study. Participants may be contacted regarding future center events or research opportunities if they consented that a member of the study team can contact them in the future on the consent form. The safeguards described above in Section 8.2 will be implemented to ensure subject confidentiality.

No identifiable data will be used for future studies without participant's consent for future use of data and without first obtaining IRB approval. The investigator will obtain a data use agreement between provider (the PI) and any recipient researchers (including others at CHOP) before sharing a limited dataset (dates and zip codes).

8.4 Regulatory and Ethical Considerations

8.4.1 Data and Safety Monitoring Plan

While there is no data monitoring safety board in place for this study as it is a study with minimal risk and without medical or biological intervention, the research teams at the University of Pennsylvania and the Children's Hospital of Philadelphia, led by the Investigators, will be aware of and will monitor possible areas of risk to the research participants. Weekly team meetings will include discussion of any safety and data issues that are observed. The PIs will be responsible for monitoring the data and safety.

8.4.2 Risk Assessment

Despite care taken in the study design to minimize risk exposure to participants, it is acknowledged that there is minimal risk to participants.

Loss of confidentiality is a potential risk of participating in this study; however, the safeguards put in place by *Way To Health* (Section 8.1) will reduce this likelihood. The members of the study teams will follow necessary precautions to ensure that all collected data is not shared with unauthorized individuals or groups.

As part of this study, teens will be driving with a cell phone blocking device present and operating in the vehicle. These teens are eligible for the study because they admit to texting while driving. This study will not require them to interact with their phones while driving any more than they would normally choose to on their own. We will encourage participants throughout the study to drive safely and not to use their cell phones while driving.

It is possible that participants may feel uncomfortable answering some of the interview questions. They will be made aware before the start of the interview that this is a risk associated with participation in the interview and will be reminded that they do not have to answer any questions which make them uncomfortable.

8.4.3 Potential Benefits of Study Participation

There are no direct benefits from participating in this study.

8.4.4 Risk-Benefit Assessment

The gathered information has the potential to increase the understanding of teen's and parent's opinions on cellphone blocking technology. The research has the potential to enhance the foundation of behavioral change models and improve the quality of continuing education about safety. The results may also speak to the benefits of using cellphone blocking devices in-vehicle for promoting positive safety behaviors; these benefits outweigh the minimal risk of participation in this study.

8.5 Recruitment Strategy

Potential participants will be recruited through a variety of strategies. As we are not limited by geographic location we will perform all recruitment strategies on a national level unless otherwise noted. These strategies consist of on-the-ground recruitment strategies (posting posters and flyers in visible areas, recruitment through local school districts), direct mailer (email blasts, letter or postcard sent to home address), social media (facebook, craigslist, snapchat, etc), for-profit and nonprofit organization partnerships/mentions, media attention (mentions in local and national news sources), and word-of-mouth referrals.

On-the-ground recruitment strategies include posting flyers in areas where teen drivers and parents frequent and recruiting through local school boards. These locations will include parks, malls, and other after school hangouts. These materials will only be posted in the Philadelphia area rather than nationwide. We will also reach out to local school boards to ask about having flyers posted and/or sent to parents in the Philadelphia. We will contact

persons in in the district superintendent office to investigate whether they will be willing to post theses flyers at schools in their district and/or are willing to mail letters to parents of teen drivers in their school district. This will only be done in the Philadelphia area. No recruitment will occur through schools or public places without first obtaining permission. Letters, postcards, and flyers will consist of the messaging in the letters, postcards, and flyer we have attached to this protocol.

We will also recruit participants by mailing letters and doing email blasts to parents of teen drivers. We will work with CHOP's Recruitment Enhancement Core (REC) to contact individuals who have visited CHOP and who have teen drivers through direct mailers of letter and/or postcards. The REC will also send email blasts to families on our behalf. These emails will consist of the messages included in the letters attached to this protocol. Recruitment efforts will include sending mailings in addition to the REC contacting them through email. Investigators will also obtain mailing labels with potential subjects' names and addresses for recruitment letters from the REC.

Social media sources will also be used for recruitment purposes. We plan to use Facebook, Craigslist, Twitter, Snapchat, Google, and Instagram in our social media campaign. The Penn Social Media & Health Innovation Lab will assist us in using the various social media outlets so that we can be as effective as possible in disseminating the recruitment message to the correct population. With many of these mediums we will be able to target teens and parents with separate ads. In those cases we will provide recruitment ads that are targeted for that specific population. In many cases the social media ad that we can use consists of a brief message (i.e., Twitter only allows a 160 character message). In these cases the message would direct the potential participant to the WTH landing page where they can register. On this page we will recreate the full message that is included in the recruitment letters so that all participants are well informed of the study details prior to registering for the study. Final advertisements and Twitter messages have been attached to this protocol.

The use of social media in this trial will include only IRB approved advertisements. These advertisements will be used on social media in a manner that does not allow commenting, posts, or conversation. They will be posted in a way that they will appear like any other advertisement. We will not be creating any social media site where posts or comments can be made (such as a facebook site) instead we will only commence with advertising this study on social media in a form where we will not have to monitor chats and comments. Only IRB approved study staff can post these ads on these sites, after discussion with the study team.

We will be reaching out to many for profit and nonprofit organizations that might be willing to help us advertise this study. These organizations include but are not limited to MADD, insurance companies, and cell phone companies (other examples: madd.org<<http://madd.org>>, vsofa.org<<http://vsofa.org>>, stoptextsstopwrecks.org<<http://stoptextsstopwrecks.org>>, aaafoundation.org<<http://aaafoundation.org>>, enddd.org<<http://enddd.org>>, digitalresponsibility.org<<http://digitalresponsibility.org>>). We will ask these organizations if they would be willing to advertise to consumers using the flyer, letter, or brief mentions on their websites. Letters and flyers would be the same as those used for other recruitment strategies. Brief mentions would redirect potential participants to the WTH landing page where they would read the full recruitment message.

We will be working with the CHOP ad UPenn media relations offices to learn various ways we might get mentions for this study in the press. We hope that some local and nationwide news outlets (Penn News Today, NPR, and other print and online newsletters) will be interested in doing a story on the goals of this program and that this media attention will help with recruitment. If we are successful in getting media attention the lead Penn PI for this study, [name], will conduct interviews and ensure that a link to the WTH landing page is included in any material produced around the study.

While all the above recruitment strategies may differ in terms of their approach, message length and type, each method will direct all potential participants either to the WTH landing page where a standard message giving an overview of the program will be posted, or to contact the study team for more information and instructions for how to enroll (via the Way to Health website). That landing page text has been included in this protocol as well. It is important to stress that because of this method all potential participants will be exposed to the same recruitment message and study information prior to registering for the program.

The Recruitment Enhancement Core provides assistance with recruitment plan development and will identify and contact potential participants on our behalf using the CHOP Data Warehouse, and the CHOP Recruitment Registry.

